4.2. Inclusion Criteria

Each subject must meet all of the following criteria to be eligible to be enrolled in this study:

1. Completed the 12-week treatment period in 1 of the 2 pivotal studies (Study DMVT-505-3001 or Study DMVT-505-3002)
2. Male or female
3. Female subjects of child-bearing potential and male subjects who are engaging in sexual activity that could lead to pregnancy should use one of the following acceptable birth control methods while on study and for 4 weeks after the last exposure to study drug. Acceptable contraception methods are:
 - Female subject or male subject's female partner is surgically sterile (bilateral tubal ligation, hysterectomy, bilateral oophorectomy) for a minimum of 3 months prior to the first dose of study drug
 - Female subject or male subject's female partner has had an intrauterine device in place for at least 3 months prior to the first dose of study drug
 - Double barrier methods (e.g., condom plus diaphragm, condom or diaphragm plus spermicide) starting at least 14 days prior to the first dose of study drug
 - Subjects who claim abstinence as their method of contraception are allowed provided they agree to use a double barrier method (e.g., condom plus diaphragm, condom or diaphragm plus spermicide) should they become sexually active from Screening to 1 month after the last dose of study drug
 - Surgical sterilization of male subject or female subject's partner (vasectomy) a minimum of 3 months prior to first dose of study drug
 - Female subject or male subject's female partner is taking hormonal contraceptives starting at least 3 months prior to the first dose of study drug. If hormonal contraceptives were started less than 3 months prior to the first dose of study drug, subjects must agree to use a double barrier method (e.g., condom plus diaphragm, condom or diaphragm plus spermicide) from Screening through 3 months after the initiation of hormonal contraceptives

These allowed methods of contraception are only effective when used consistently, correctly and in accordance with the product label. The Investigator is responsible for ensuring that subjects understand how to properly use these methods of contraception.

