6.3. Safety Assessments

6.3.1. Adverse Events

All AEs will be collected from the time the subject signs the ICF until the final visit/contact with the subject. Adverse events that began during the pivotal study and were ongoing at the end of that study will be reported as ongoing AEs. Additional safety information, including the definition of an AE and the methods for recording, evaluating, and assessing causality of AEs and the procedures for completing and transmitting SAE reports are provided in Section 8.

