8. HANDLING OF MISSING DATA

Efficacy endpoints will be summarized by visit using observed cases (OC) and last observation carried forward (LOCF) methods as appropriate. Baseline values will not be carried forward.

Imputation of Start and End Dates of Adverse Event (AE)

To calculate duration of Adverse Events, the following rules will be used where applicable to impute partial or completely missing start dates or end dates:

- If only the day is missing for a start date, the 1st of the month will be imputed. If the new estimated date falls before the Visit 1 date, while the known month and year match the month and year of the Visit 1 date, the date of Visit 1 will be used as the new estimated date.
- If only the day is missing for an end date, the last day of the month will be imputed. If the new estimated date falls after the date of last study visit, the date of last study visit will be used as the new estimated date.
- If both the day and the month are missing for a start date or end date, no imputation will be used, and the duration will not be calculated.
- If the start date or end date is completely missing, duration will not be calculated.

For AEs ongoing at the end of pivotal studies, duration will be computed using the DMVT-505-3003 visit 1 date as the AE start date.

If relationship of AE to treatment is missing, the event will be conservatively considered as being related to study drug. Missing AE severity will be imputed to the highest severity level (most severe). Through the data cleaning process, all attempts will be made to avoid missing values for relationship and severity.

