10.3 Study Day

Day 1 is the date of Visit 1 (which is also the last visit in pivotal studies). Study day is calculated relative to the date of Day 1.

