11.11.1 Adverse Events

AE terms will be coded using Medical Dictionary for Regulatory Activities (MedDRA) dictionary. All AEs reported in current study are considered as treatment-emergent AE (TEAE) except for those AEs ongoing at the end of pivotal studies but resolved prior to the Visit 1 date in the extension study.

All TEAEs will be listed by subject, detailing the verbatim term given by the investigator, the preferred term (PT), system organ class (SOC), onset date and time, end date and time, ongoing at the end of pivotal studies (Y/N), duration (days), CTCAE grade, outcome, relationship to study drug, action taken with study drug, other action taken to treat the event, AE of special interest (Y/N), seriousness and criteria for seriousness.

AEs resolved prior to the Visit 1 date, Serious TEAEs (STEAEs), TEAEs leading to study discontinuation and TEAEs related to study drug will also be listed separately. The following adverse events of special interest (AESIs) will be identified and listed separately: contact dermatitis, folliculitis, and headache.

The number and percent of subjects with TEAEs will be summarized as incidence rates of:

- Any TEAE
- Any TEAE Excluding Those Ongoing at the end of the Pivotal Studies
- Any TEAE Ongoing at the end of the Pivotal Studies
- Any treatment-emergent AESIs
- Any treatment-emergent AESIs Excluding Those Ongoing at the end of the Pivotal Studies
- Any treatment-emergent AESIs Ongoing at the end of the Pivotal Studies
- Any treatment-related TEAE
- Any TEAE leading to study drug discontinuation
- Any TEAE leading to study discontinuation
- Any serious TEAE

- Death
- Treatment-related Serious TEAE
- Serious TEAE leading to study drug discontinuation
- Serious TEAE leading to study discontinuation
- TEAE (COVID-19)

Individual PTs will be summarized by SOC in alphabetical order and PT in descending order of frequency for the following subsets and subgroupings:

- All TEAEs
- All TEAEs by maximum CTCAE grade
- All TEAEs by maximum causality (not related, related) to the study drug
- All TEAEs Excluding Those Ongoing at the End of the Pivotal Studies
- All TEAEs ongoing at the end of the pivotal studies
- All treatment-related TEAEs
- All TEAEs leading to study discontinuation
- All TEAEs leading to study drug discontinuation
- All serious TEAEs

All TEAEs and all serious TEAEs will also be summarized by SOC (alphabetical order) and PT (descending order) for the following subgroups:

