- Age (<65 and \geq 65 years old)
- Sex
- Race (White, Other)

Furthermore, TEAEs will be categorized by day of onset among the following 4 categories:

- \leq 12 weeks
- >12 to \leq 24 weeks
- >24 to \leq 40 weeks
- >40 weeks.

For each of these categories, TEAEs will be summarized by SOC in alphabetical order and PT in descending order of frequency. TEAEs ongoing at the end of the pivotal studies will be considered in the first category (i.e. day of onset \leq 12 weeks).

At each level of summarization, a subject will be counted once if he/she reported one or more events. The severity of TEAEs and relationship to study drug will be summarized in a similar

manner. For summaries of relationship to study drug, a subject will be classified according to the closest relationship. For summaries of TEAE CTCAE grade, a subject will be classified according to the worst grade.

For AESIs, summarization will be more extensive, reflecting the more detailed information collected. Information summarized will include number of events per subject, earliest onset day, duration (in days), causality, grade and seriousness of AESIs, outcome, actions taken, assorted physical characteristics of the AESIs, and demographic/baseline characteristics and PGA status of the subjects experiencing them. Each type of AESI will be summarized separately. If a subject has more than one treatment-emergent occurrence of an AESI, the subject's maximum duration, highest levels of causality and seriousness, maximum grade and generally the most extreme level of each characteristic will be summarized. If an AESI was ongoing at end of study (EOS), it will not be included in the duration summary. AESIs ongoing at the end of pivotal studies will also be included in the summary.

A Kaplan-Meier figure will be generated for each AESI of time to first event for events starting during the study. Subjects not experiencing the AESI will be censored at the date of study completion or discontinuation. AESIs ongoing at the end of pivotal studies will not be included.

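### Durations of adverse events carried over from the pivotal studies are counted from extension Visit 1, then pooled with full durations of new events in the AESI maximum-duration summary

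*SAP*

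**What the plan says.** Protocol 6.3.1 brings unresolved pivotal-study events into this study: "Adverse events that began during the pivotal study and were ongoing at the end of that study will be reported as ongoing AEs". SAP 11.11.1 then treats them as events of this study: "All AEs reported in current study are considered as treatment-emergent AE (TEAE) except for those AEs ongoing at the end of pivotal studies" but resolved before Visit 1. An event still present at Visit 1 is therefore treatment-emergent here.

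The duration rule is in SAP 8: "For AEs ongoing at the end of pivotal studies, duration will be computed using the DMVT-505-3003 visit 1 date as the AE start date". It follows a list of rules for partial or missing dates, but nothing restricts it to events with such dates.

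SAP 11.11.1 gives the AESIs (contact dermatitis, folliculitis, headache) a fuller summary that includes duration in days. Three of its rules matter here:

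- Carried-over events are in: "AESIs ongoing at the end of pivotal studies will also be included in the summary".
- A subject with several occurrences is represented by "the subject's maximum duration, highest levels of causality and seriousness, maximum grade", and generally by the most extreme level of each characteristic.
- Events still open at the end are out: "If an AESI was ongoing at end of study (EOS), it will not be included in the duration summary".

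The treatment-emergent event listing shows onset date, end date, carry-over flag and duration together. Neither document plans a duration summary from pivotal-study onset.

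**The concern.** For a carried-over event the rule yields the time remaining after Visit 1; for a new event it yields the time from onset to resolution. These are different quantities, and the AESI summary puts them in one distribution with no split or label.

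The shortening does not fall at random. An event is more likely to straddle the handover if it lasts longer, so carried-over events are on average longer than events in general. The rule also works against the SAP's stated aim of reporting each subject's most extreme value, because a shortened event can be displaced as the maximum by a briefer new one. It sits awkwardly beside the other choices in SAP 8, where missing causality is set to related and missing severity to the highest grade. Those choices lean towards caution; this one leans the other way.

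At stake is the reported persistence of the three AESIs. Protocol 8.1.3 asks sites to collect duration for each of them.

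**Working it through.** The plan states no figure for event duration or for the shortening, so there is nothing to reproduce. The check is date arithmetic.

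**Inputs**

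- Start date used for carried-over events: Visit 1 (SAP 8).
- Visit 1 is Day 1 of the extension and also the last pivotal visit (SAP 10.3).
- Pivotal treatment lasts 12 weeks, or 84 days: "Completed the 12-week treatment period in 1 of the 2 pivotal studies" (Protocol 4.2). With pivotal treatment starting on Day 1, Visit 1 is pivotal Day 85.
- Counting convention: end minus start plus 1. The SAP does not state this for event duration, so it is an assumption; the 1 cancels in the difference.

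**Formulas**

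- Duration under the SAP = end − Visit 1 + 1
- Duration from onset = end − onset + 1
- Shortfall = Visit 1 − onset

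The shortfall does not depend on when the event ends. It is 1 day for onset the day before Visit 1 and 85 − 1 = 84 days for onset on pivotal Day 1. If the extension's ±3-day visit window is assumed for the pivotal Week 12 visit, the ceiling is 81 to 87 days.

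**Range for resolved events** (SAP duration → duration from onset, and percent understated)

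| Onset before Visit 1 | Ends extension Day 29 | Ends Day 85 | Ends Day 281 |
|---|---|---|---|
| 1 day | 29 → 30 (3%) | 85 → 86 (1%) | 281 → 282 (0%) |
| 7 days | 29 → 36 (19%) | 85 → 92 (8%) | 281 → 288 (2%) |
| 28 days | 29 → 57 (49%) | 85 → 113 (25%) | 281 → 309 (9%) |
| 56 days | 29 → 85 (66%) | 85 → 141 (40%) | 281 → 337 (17%) |
| 84 days | 29 → 113 (74%) | 85 → 169 (50%) | 281 → 365 (23%) |

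**Effect on the subject's maximum (constructed example).** Folliculitis starts on pivotal Day 15 and resolves on extension Day 15, which is pivotal Day 85 + 14 = 99.

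- From onset: 99 − 15 + 1 = 85 days.
- Under the SAP: 99 − 85 + 1 = 15 days.
- Shortfall: 85 − 15 = 70 days, and 70/85 = 82%.

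If the same subject later has a new 20-day episode, the SAP maximum is max(15, 20) = 20 days. From onset it is max(85, 20) = 85 days.

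**Average effect (illustration only).** Assume onsets uniform over the 84 days and exponential durations. Neither assumption comes from the documents.

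| Mean duration, all events | Carried-over, from onset | Carried-over, SAP rule | Mean shortfall |
|---|---|---|---|
| 14 days | 27.9 | 14.1 | 13.8 |
| 28 days | 51.7 | 28.0 | 23.7 |
| 56 days | 87.9 | 56.0 | 31.9 |
| 112 days | 148.6 | 111.8 | 36.8 |

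Under this model carried-over events truly last longer than events in general, yet the SAP rule makes their mean look the same as that of all events.

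**The case against.** The strongest reply is that this is a convention stated openly. Time in this study runs from Visit 1, and SAP 11.11.1 likewise assigns carried-over events to the earliest onset category. No sentence calls the result duration from onset. Former vehicle subjects were not on tapinarof before Visit 1, so counting from pivotal onset would bring vehicle time into a tapinarof extension table. That last point stands, and it is why results should be shown by pivotal treatment group. It does not justify mixing two quantities in one column, and a footnote alone would leave the maximum in the example at 20 days.

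A second reply is that the onset date may not be available. The documents do not say that the listed onset date of a carried-over event is the pivotal one. This also stands: availability is inferred, and a merge with pivotal data may be needed.

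A third reply is that the reach is small. Subjects whose pivotal-study event led to permanent discontinuation are excluded (Protocol 4.3). Protocol 10.4.3 plans no duration analysis, and the study is descriptive with no testing. Incidence is shown with, without and only for carried-over events, and the AESI Kaplan-Meier figure leaves them out. All of this is correct and limits the point to the duration output. It also shows that the SAP already separates carried-over events in its incidence overview, but not in the duration summary.

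A reader might go further and infer that the longest events are all reported about 12 weeks too short. The documents do not support that. Eighty-four days is a ceiling for events starting during pivotal treatment, a short event that happens to span Visit 1 loses only days, and AESIs still open at end of study are dropped from the duration summary rather than shortened. Long new-onset events are not shortened either.

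**Conclusion.** The point holds for carried-over events that resolve during the study. Followed as written, the SAP understates each one's duration by Visit 1 minus onset, between 1 and about 84 days for onset during pivotal treatment, and can report the wrong event as a subject's maximum AESI duration. The direction is certain. The total effect is not, because neither document gives the number of carried-over events or their onset dates. The average shortfall of roughly 14 to 37 days belongs to the illustrative model, and the 82% belongs to one constructed case.

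The 84-day ceiling rests on 12 weeks of pivotal treatment and on Visit 1 coinciding with the last pivotal visit. It would be higher if Visit 1 came later, or if events that began before the first pivotal dose were also carried over; the documents do not settle either. The conclusion does not extend to incidence, severity, causality or the time-to-first-AESI curves. It should be corrected before the AESI tables are produced, as a fault in a secondary descriptive safety output.

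**What to change.** In SAP 8, replace the sentence with a rule that the duration of carried-over events, including AESIs, is computed from the onset date recorded in the pivotal study. Apply the existing partial-date rules to these events without the reset to Visit 1. Use this duration for the AESI maximum.

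In SAP 11.11.1, summarize AESI duration separately for carried-over and new-onset events, by double-blind treatment group, so that pre-Visit 1 time on vehicle is visible. If a Visit 1-based figure is also wanted, give it its own column labelled *days during DMVT-505-3003* and keep it out of the maximum.

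The cost is a merge with pivotal adverse event dates if onset is not already in the extension data, plus one more split in the AESI tables. Reported AESI durations will be somewhat longer, and for former vehicle subjects they will include days on vehicle.

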8.2. Classification of Adverse Events

8.2.1. Assigning Severity Rating for Adverse Events

8.2.1.1. Criteria for Determining Adverse Event Severity

The Investigator will make an assessment of the severity of each AE and SAE according to the National Cancer Institute Common Terminology Criteria for Adverse Events (CTCAE), v. 5.0, 2017. For terms not specified with the CTCAE, the criteria in [Table 4](#) should be used to determine the grade severity.

Table 4: Criteria for Determining the Grade/Severity of Adverse Event Terms Not Specified by the National Cancer Institute CTCAE

Grade	Criteria
1	Mild; asymptomatic or mild symptoms, clinical or diagnostic observations only; intervention not indicated
2	Moderate; minimal, local, or noninvasive intervention indicated; limiting age-appropriate instrumental activities of daily living ^a
3	Severe or medically significant but not immediately life-threatening; hospitalization or prolongation of hospitalization indicated; disabling; limiting self-care activities of daily living ^b
4	Life threatening consequences; urgent intervention indicated
5	Death related to adverse event

CTCAE = Common Terminology Criteria for Adverse Events.

^a Instrumental activities of daily living refer to preparing meals, shopping for groceries or clothes, using the telephone, managing money, etc.

^b Self-care activities of daily living refer to bathing, dressing and undressing, feeding self, using the toilet, taking medications, and not bedridden.

Adverse event severity should be recorded in the appropriate section of the adverse event case report form and in the subject's source documents.

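### The SAP sets a missing AE severity to the top level without regard to outcome, so an ungraded non-fatal AE could be counted at Grade 5

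*SAP*

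**What the plan says.** SAP section 8 (Handling of Missing Data) gives two default rules for incomplete AE records. For severity: "Missing AE severity will be imputed to the highest severity level (most severe"). For missing causality, "the event will be conservatively considered as being related to study drug". The same paragraph undertakes to keep both kinds of missing value to a minimum through data cleaning. The severity rule names no grade, sets no ceiling and does not mention the outcome of the event.

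Protocol section 8.2.1.1 fixes the severity scale as the "Common Terminology Criteria for Adverse Events (CTCAE), v. 5.0, 2017". It continues "For terms not specified with the CTCAE, the criteria in" Table 4 are to be used. Table 4 runs from Grade 1 to Grade 5, and Grade 5 is defined as "Death related to adverse event".

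SAP section 11.11.1 plans a table of "All TEAEs by maximum CTCAE grade" and adds: "For summaries of TEAE CTCAE grade, a subject will be classified according to the worst grade". For AESIs with more than one occurrence in a subject, the "maximum grade and generally the most extreme level of each characteristic will be summarized".

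Death is captured elsewhere too. Protocol section 8.3.2 has Fatal as one of the AE outcome categories, and the TEAE overview in SAP section 11.11.1 has its own row for Death.

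**The concern.** A worst-case default is reasonable when the worst case is a value the event could have had. That holds for causality: any event might have been judged related. It does not hold for the top of a grade scale whose last level records that the subject died. Whether the subject died is already known from the outcome field, so giving Grade 5 to an event with a recorded non-fatal outcome asserts something the data contradict.

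Safety is the first objective of this study, and the grade table is one of its main safety displays. A Grade 5 entry with no matching death would have to be traced and explained in the study report, and possibly earlier, because a data-cut is planned for the marketing application (protocol section 10.5, SAP section 9) and the SAP gives no separate rule for it.

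**Working it through.** The documents state no figure to reproduce. The check sets the rule beside the scale and the outputs that use it.

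1. **Input.** An AE has no severity recorded. Its outcome is, for example, Recovered/Resolved (a category in protocol section 8.3.2).
2. **Rule (SAP section 8).** Severity becomes the highest level. No condition on outcome applies.
3. **Scale (protocol section 8.2.1.1).** For a term outside the CTCAE, the highest level is Grade 5 in Table 4. For a term listed in the CTCAE, the top grade is not printed in these documents and cannot be confirmed here.
4. **Maximum-grade table (SAP section 11.11.1).** A subject is counted once at each level of summary, at the worst grade. The imputed Grade 5 therefore displaces any lower recorded grade at every level that contains the event: its preferred term, its system organ class, and any all-events row.
5. **AESI summary (SAP section 11.11.1).** This takes the subject's maximum grade, so an ungraded AESI is affected in the same way if its scale reaches Grade 5.
6. **Listing.** The TEAE listing prints CTCAE grade and outcome for each event. The SAP does not say whether the grade shown is the recorded or the imputed one. SAP section 10.1 has derived variables listed when they are summarised, so the imputed grade may appear there too.
7. **Items left alone.** The severity rule is not stated to alter the Fatal outcome or the Death row.

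**Size.** The documents give no rate of missing severity, so the number of affected subjects k is an assumption. With the planned enrolment of about 850 (SAP section 6), and no actual deaths, the Grade 5 share is k / 850:

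- k = 1: 1/850 = 0.12%
- k = 3: 3/850 = 0.35%
- k = 5: 5/850 = 0.59%

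In each case the Death row would read 0.

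**The case against.** The best defence is that the rule speaks of a severity level, not of a CTCAE grade. Protocol section 8.1.3 collects AESI severity as mild, moderate or severe, and Table 4 attaches the word severe to Grade 3, while Grade 5 describes an outcome rather than an intensity. On that reading the author meant severe and never had death in mind. In addition, the protocol requires severity to be recorded on the case report form, the SAP promises to chase missing values, all analyses are descriptive, and a listing that shows grade beside outcome would expose any mismatch.

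Most of this bears on how often the problem occurs, and it stands: the case should be rare, and no test or estimate depends on it. The alternative reading does not remove the problem. The SAP reports severity as CTCAE grade and nowhere ties the rule to a three-level scale. If severe was intended, the SAP still has to say which grade that is.

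Three stronger claims are tempting and are not supported:

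- **A false death count.** A reader might infer that a non-fatal AE would be tabulated as a death. It would be tabulated at the fatal grade; the outcome and the Death row are unchanged.
- **A treatment-related Grade 5 table entry.** A reader might combine the two defaults in SAP section 8. The planned tables by maximum grade, by maximum causality and of treatment-related events are separate, and none crosses relationship with grade. At most a listing row could show both values, and only if the event were ungraded and also either judged related or missing causality.
- **Grade 5 for every term.** The documents show this level only for the Table 4 scale.

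**Conclusion.** The point holds in limited form. As written, the severity rule can put an ungraded, non-fatal AE at Grade 5 in the maximum-grade table and the AESI grade summary, and possibly in the listing. That would displace recorded grades and conflict with the outcome field and the Death row. This is a stated rule that gives a wrong result when followed, not a missing detail.

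The conclusion assumes that the rule is applied literally to the CTCAE-graded variable, that at least one severity stays missing after cleaning, and that the term's scale reaches Grade 5. The last is shown for Table 4 terms and cannot be verified here for terms in the CTCAE. The likely size is a handful of subjects or none. The severity of the finding is the lowest: worth correcting before database lock, with no bearing on the design or on any efficacy result. The companion default for missing causality is acceptable.

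**What to change.** Amend the sentence in SAP section 8 so that a missing severity is set to Grade 5 only if the AE outcome is Fatal. For any other outcome, choose one of two options and state it:

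- impute the highest non-fatal grade, which is Grade 4 in Table 4; or
- show the event in a separate missing-grade category.

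In either case, flag imputed grades in the TEAE listing so that recorded and imputed values can be told apart.

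The outcome is already collected, so no new data and no protocol amendment are needed. The cost is one more condition in the derivation. Imputing Grade 4 keeps the SAP's conservative intent but still overstates severity. It could also look inconsistent with the Grade 4 management text in protocol section 8.2.1.2.3 for a subject who stayed on study drug, which is a further reason for the flag. The missing-grade category avoids inventing a grade, at the price of an extra row in the table.
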